### **Last contact/participation date**

The last contact/participation date for a subject is the last available date across all the data collected for that subject. For a subject with a death event, the date of death will be used.

#### **2.1.2 Decimal places**

The rules for decimal places in data presentation are the following:

- All percentages and their confidence intervals will be presented to one decimal place.
- Standard errors and standard deviations: data precision + 2 decimal places
- Means, medians and quartiles: data precision + 1 decimal place
- Minimums and maximums: same as data precision
- Data precision of BMI will be 1 decimal place.
- Total subject-years of exposure will keep one decimal place.

### **2.2 Analysis sets**

The safety population will be used for data analyses and/or presentation.

#### **Safety Population**

All ORION-3 rollover subjects who signed the informed consent to ORION-8, and all ORION-9/10/11 rollover subjects with at least one study drug administration in ORION-8 will comprise the Safety Population. Treatment classification will be based on the actual treatment groups of the feeder studies (Phase III Inclisiran-Inclisiran, Phase III Placebo-Inclisiran, ORION-3 Rollover). This will be the primary population for the efficacy and safety analyses.

#### **2.2.1 Subgroup of interest**

In general, no subgroup analysis will be performed. Selected analyses in [Section 2.7.4](#) for diabetes will be subgrouped by baseline diabetes or glucose control status.

### **2.3 Subject disposition, demographics and other baseline characteristics**

#### **2.3.1 Subject disposition**

The following information will be summarized for the Safety Population overall and by treatment group of the feeder studies:

- The number of subjects in each analysis population
- The number of subjects by country and site

- The number of subjects who completed the study and discontinued early, with reasons for discontinuation
- The duration on study (days)
- Protocol deviations and violations of subject restrictions

Completers are defined as subjects indicated in the EOS page of eCRF to have completed the study. This will include ORION-9/10/11 rollover subjects who have completed the Day 1080 visit, and ORION-3 rollover subjects whose study duration is shortened to < 3 years by the administrative decision only.

The duration on study is defined as the number of days from Day 1 of ORION-8 to the date of last recorded contact/participation date in the database.

### **2.3.2 Demographics and other baseline characteristics**

The following demographics and baseline characteristics will be summarized for the Safety Population overall and by treatment group of the feeder studies:

- Age (years) using descriptive statistics
- Age categories:  $\geq 18$  - <65,  $\geq 65$
- Age categories:  $\geq 18$  - <50,  $\geq 50$  - < 65,  $\geq 65$  - < 75,  $\geq 75$
- Gender
- Child-bearing potential of females
- Weight (kg)
- Height (cm)
- Body mass index (BMI) (kg/m)
- Race
- Ethnicity
- Country
- Baseline estimated glomerular filtration rate (eGFR) (mL/min/1.73m)
- Baseline eGFR categories:  $\geq 15$  - < 30,  $\geq 30$  - <60,  $\geq 60$  - <90,  $\geq 90$
- Medical history (targeted and other medical history)

For categorical variables in the list above, the percentages will be calculated based on total number of subjects (N) in a particular treatment group including subjects with a missing value. Subjects with a missing value will be counted in “Missing” category.

Age at ORION-8 baseline will be calculated by (age collected at ORION-1/9/10/11 screening) + floor[(ORION-8 consent date – ORION-1/9/10/11 consent date)/365.25], where floor(x) is the largest integer less than or equal to x.

Gender, race, and ethnicity will be taken from the data collected at ORION-1/9/10/11 screening. Country will be based on the subject's participation site in ORION-8.

For child-bearing potential of females, the percentages are out of the number of female subjects. If a female was determined not to have child-bearing potential in the feeder study, the subject will also have no child-bearing potential in ORION-8. If a female was determined to have child-bearing potential in the feeder study, the subject's child-bearing potential will be re-evaluated at ORION-8 Day 1 and the result of the re-evaluation will be used.

The height collected at ORION-1/9/10/11 screening will be used as the baseline value for ORION-8, as no significant change in adult subjects' height is expected.

The last available weight in ORION-3/9/10/11 will be used as the baseline value for ORION-8. The BMI, which equals to weight in kilogram divided by (height in meter), will be calculated based on this weight.

The baseline eGFR will use ORION-8 baseline data.

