3.1 Type/Design of Study

[figure not shown]
This study will be a long-term extension of the Phase II lipid lowering trial [MDCO-PCS-16-01 (ORION-3)] and Phase III lipid-lowering studies [MDCO-PCS-17-03 (ORION-9), MDCO-PCS-17-04 (ORION-10), or MDCO-PCS-17-08 (ORION-11)]. Up to 3300 subjects with atherosclerotic cardiovascular disease (ASCVD), ASCVD-risk equivalents (eg, diabetes and familial hypercholesterolemia), heterozygous [REDACTED] familial hypercholesterolemia (HeFH [REDACTED]) and elevated LDL-C despite treatment with LDL-C lowering therapies who are eligible and willing to participate may be enrolled. The objectives of the study is to evaluate the efficacy, safety, and tolerability of long-term dosing of inclisiran. Informed consent will be obtained from subjects before the initiation of any study-specific procedures. The EOS visit in the previous feeder studies will be Day 1 in the extension trial except for subjects enrolled in Sweden. Sweden Specific Protocol Amendment 1 (to Global Amendment 1 version, dated 1 Nov 2018) was implemented to allow limited lab tests to be done on Day 1 and to collect any safety information during the gap between feeder's EOS and Day 1 of this study until ethics committee approval was granted in that country. Subjects moving over from the open label ORION-3 study will not receive study medication at Day 1. Their first dose of study medication in this trial will be at day 90. This is to maintain their 6 months dosing schedule on inclisiran treatment. This trial will be a global, multicenter study in approximately 300 centers.

The duration that each subject is expected to participate in this study is a maximum of 3 years or the occurrence of one of the following events, whichever occurs first:

- a recommendation of discontinuation by the investigator or Sponsor,
- a decision by the subject to discontinue for any reason,
- an administrative decision is made to end the study

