4. Vital signs: blood pressure and heart rate will be measured prior to injection on dosing days. When available, an automated BP device is recommended for collection of BP and the result recorded to the nearest mmHg. The subject should be sitting at rest for at least 5 minutes prior to these assessments. One assessment for each vital sign (HR, BP) is required per applicable visit.
5. See [Section 7.1.6.3](#) for details of specific tests to be analyzed
6. See [Section 7.1.6.1](#) and [Section 7.1.6.2](#) for details of specific tests to be analyzed
7. Urinalysis collection is prior to the injection; supplies from the central laboratory must be used to perform the urinalysis
8. Only in women of childbearing potential (performed locally, prior to any dosing, using central laboratory kit supplies and with results prior to injection; urine pregnancy test). Results of the pregnancy test from Day 540 of the feeder study will be used on Day 1 in ORION-8
10. Subjects who received blinded placebo in the feeder study will receive blinded inclisiran and subjects who received blinded inclisiran in the feeder study will receive blinded placebo on Day 1 in ORION-8. Subjects moving over from the ORION-3 trial will not receive any treatment at Day 1; all subjects were on inclisiran in the feeder trial and will receive their first dose of inclisiran in this study at day 90
11. Subjects will be observed in the clinic for 30 minutes post injection in order to have additional vital and/or laboratory assessments completed if needed. For any suspected episode of anaphylaxis, the investigator will need to collect a blood sample for tryptase within 30 minutes of an onset of anaphylaxis (or as soon as logically possible).
12. Concomitant medications (relevant) and AE/SAE collection for this study will begin at time of consent and continue through EOS. Ongoing concomitant medications and AEs/SAEs from the feeder study will continue to be followed in this study until resolution.

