10.3 Statistical Analyses

10.3.1 Demographic and Background Characteristics

Subject demographics and baseline characteristics except age collected from prior corresponding Phase III studies for each subject will be used for the summary using the safety population. For subjects moved over from the Phase II ORION-3 study, subject demographics and baseline characteristics collected at the ORION-3 study baseline will be used for this summary. Age will be recalculated by adding the duration that each subject spent in the prior corresponding Phase II or Phase III study

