## **4 Change to protocol specified analyses**

No change from protocol specified analysis was made.

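### The SAP age formula drops the part-year between feeder and ORION-8 consent, so about half of Phase III rollovers are reported one year too young (descriptive tables only)

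*SAP*

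**What the plan says.** The rule in SAP 2.3.2 begins "Age at ORION-8 baseline will be calculated by (age collected at ORION-1/9/10/11 screening" and adds the number of days from feeder consent to ORION-8 consent, divided by 365.25 and floored, "where floor(x) is the largest integer less than or equal to x". For ORION-3 rollovers the starting point is ORION-1 screening, so their interval runs from ORION-1 consent.

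The same section summarises "Age (years) using descriptive statistics" and two sets of age bands, one cut at 65 and the other at 50, 65 and 75. Both are shown overall and by feeder treatment group.

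Protocol 10.3.1 describes the derivation more loosely: "Age will be recalculated by adding the duration that each subject spent in the prior corresponding Phase II or Phase III study". It gives no unit, precision or rounding rule. SAP section 4 states: "No change from protocol specified analysis was made".

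**The concern.** An age in completed years has already lost the time since the last birthday. Flooring the interval discards a second part-year. When the two lost parts together reach a full year, a birthday has been missed and the derived age is one year low. No combination makes it high.

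Example: a subject aged 63.75 at feeder consent is recorded as 63. After 540 days (1.478 years) the true age is 65.228, or 65 completed years. The SAP formula gives 63 + 1 = 64 and places the subject in the under-65 band.

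Because the error runs in one direction, it does not average out in a large study. At stake are the reported mean age and the counts in the older bands of the baseline table.

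**Working it through.** The plan states no figure for this point, so there is none to reproduce.

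**Inputs**
- Collected age: taken as completed years. This is an assumption; the SAP does not say so, but adding a whole number of years suggests it.
- Phase III interval: Protocol 3.1 says "The EOS visit in the previous feeder studies will be Day 1 in the extension trial except for subjects enrolled in Sweden", and note 8 to Protocol Table 6-1 says "Results of the pregnancy test from Day 540 of the feeder study will be used on Day 1 in ORION-8". Together these put ORION-8 Day 1 at about feeder Day 540. Swedish subjects had a further gap of unstated length.
- Feeder screening time: the formula runs from consent, so screening time is added. Its length is not given; 0 to 45 days is assumed.
- ORION-3 interval, from ORION-1 consent: not given.

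**Formula**

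Let true age at feeder consent be a + f, with a in whole years and f uniform on 0 to 1. Let the interval be n + g years, with n whole and g the remaining fraction.
- SAP age = a + n.
- True completed age = a + n + floor(f + g).
- The SAP is one year low when f + g ≥ 1, which has probability g. The mean error against completed years is therefore −g, whatever the distribution of age in whole years.

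**Phase III rollovers**

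| Assumed screening (days) | Interval (days / 365.25) | One year low | Mean error (years) |
|---|---|---|---|
| 0 | 540 / 365.25 = 1.478 | 47.8% | −0.48 |
| 14 | 554 / 365.25 = 1.517 | 51.7% | −0.52 |
| 28 | 568 / 365.25 = 1.555 | 55.5% | −0.56 |
| 45 | 585 / 365.25 = 1.602 | 60.1% | −0.60 |

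A simulation of 2,000,000 subjects agrees with these values. Spreading visits by ±30 days, with 0 to 28 days of screening, gives 51.7%.

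**ORION-3 rollovers**

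The share equals the fractional part of an unknown interval. An interval of exactly 4 years would give 0%, 4.25 years 25% and 4.75 years 75%.

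**Age bands**

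A subject is misplaced at 65 when true age at ORION-8 consent lies between 65 and 65 + g. These figures need an assumed distribution of age at feeder consent:
- Mean 64, SD 10, 540 to 585 days: 1.9-2.4% on the wrong side of 65; 3.7-4.6% in the wrong one of the four bands.
- Mean 65, SD 9, 540 to 570 days: 2.1-2.5% on the wrong side of 65; 1.4-1.5% on the wrong side of 75.

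For scale only, 2% of the 2991 subjects given as enrolled in the protocol's Amendment 2 rationale is 0.02 × 2991 ≈ 60. That count is not the Safety Population.

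**If the floor is simply removed**

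The age becomes a + n + g. Since floor(f + g) averages g, the mean error against completed years is 0. The bands do not move: a and n are whole numbers and g is below 1, so a + n + g ≥ 65 exactly when a + n ≥ 65.

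**Sensitivity to the completed-years assumption**
- If age was collected as a decimal, the same share g is still a completed year low.
- If it was rounded to the nearest year, most of the error disappears: about 2% are one year high with no screening time, and about 10% one year low with 45 days.

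**The case against.** The strongest reply is that this is a disclosed, reproducible convention in a non-comparative demographic table. SAP 2.2.1 plans no age subgroup, and age enters no efficacy or safety analysis. That stands, and it limits the point to a minor one.

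A reader might infer that the SAP contradicts the protocol and that its section 4 statement is therefore false. The documents do not support that. Protocol 10.3.1 does not say how the duration is to be expressed, and Protocol section 10 leaves detailed specifications to the SAP. The difference is one of wording. It does show that a decimal interval fits the protocol text more closely than a floored one.

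A reader might also blame the floor for the misplaced age bands. That is not right either: where only a whole-number age is available, the bands come out the same with or without the floor. The cause is the truncated starting age.

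Finally, the remedy that works best needs birth data. SAP 2.3.2 speaks only of an age collected at screening, and nothing in the documents shows that a birth date, or birth year and month, is held. This limits the remedy. It does not remove the bias in the mean.

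**Conclusion.** The point holds as a minor one. Assuming collected age is in completed years and feeder screening lasted 0 to 45 days, the formula makes about 48-60% of Phase III rollovers one year too young and lowers their mean age by about 0.5-0.6 year. About 2% of subjects fall on the wrong side of 65; that figure also rests on an assumed age distribution with mean 64-65 and SD 9-10.

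It would be tempting to say that half of all subjects are affected. The documents do not give the ORION-1-to-ORION-8 interval, so for ORION-3 rollovers the share is unknown, from 0 to nearly 100%. The bias may therefore differ between the displayed groups. No efficacy or safety conclusion depends on it.

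**What to change.** In SAP 2.3.2, replace the formula with a two-step rule:

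1. Where the feeder databases hold a birth date, compute completed years from birth to ORION-8 consent. Where they hold only birth year and month, do the same with a stated convention for the day. This corrects both the mean and the age bands.
2. Where only a whole-number age is held, drop the floor and add the interval as a decimal, in line with the wording of Protocol 10.3.1. This corrects the mean only. Add a footnote that the age bands still rest on a truncated age and slightly under-count the older bands.

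The SAP should also state whether the collected age is in completed years.

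The cost is a line or two of SAP text and code, plus a check of which birth data the feeder databases contain. The SAP's document history places it before database lock. If step 2 applies, the age bands cannot be fully corrected.

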### **Medical History**

Medical history (targeted and other medical history) from the initial feeder studies (ORION-1/9/10/11) will be summarized for the Safety Population overall and by treatment group of the feeder studies. For other medical history, the sites are allowed to report in ORION-8 eCRF any relevant medical or surgical issues that occurred prior to consent in the initial feeder study but were not recorded in the feeder study, and such information added in ORION-8 eCRF should be combined with other medical history from feeder trial databases. Other medical history will be coded into Medical Dictionary for Regulatory Activities (MedDRA) terminology using the most recent MedDRA version before database lock (DBL), and will be summarized by primary system organ class (SOC) and preferred term (PT).

For targeted medical history, the following data will be summarized:

- Smoking status: Current, Former, Never, Unknown
- Hypertension: Yes, No, Unknown
- Hyperlipidemia: Yes, No, Unknown
- Congestive heart failure: Yes, No, Unknown
- Diabetes mellitus: Yes, No, Unknown
- ASCVD status: ASCVD, ASCVD risk equivalent
- Prior or current CHD (Coronary Heart Disease): Yes, No, Unknown
- Prior or current CVD (Cerebrovascular Disease): Yes, No, Unknown
- Prior or current PAD (Peripheral Artery Disease): Yes, No, Unknown
- Family history of coronary artery disease: Yes, No, Unknown
- Family history of dyslipidemia: Yes, No, Unknown

A subject is classified as ASCVD if CHD = Yes or CVD = Yes or PAD = Yes. Otherwise, the subject is ASCVD risk equivalent.

In ORION-11, the questions for CHD, CVD and PAD are asked only when the subject is indicated as ASCVD in the subject type CRF question (only ORION-11 CRF has this question). Therefore, for ORION-11 subjects who are indicated as ASCVD risk equivalent, their answers to CHD, CVD and PAD questions are all implicitly “No”.

For ORION-3 rollover subjects, CHD and CVD are derived as follows:

- CHD:
  - If prior PCI (Percutaneous Coronary Intervention) = Yes or prior MI (Myocardial Infarction) = Yes or prior CABG (Cardiovascular Arterial Bypass Graft) = Yes, then CHD = Yes.
  - Else if prior PCI = Unknown or prior MI = Unknown or prior CABG = Unknown, then CHD = Unknown.
  - Else CHD = No.
- CVD:
  - If prior stroke = Yes or prior TIA (Transient Ischaemic Attack) = Yes, then CVD = Yes.
  - Else if prior stroke = Unknown or prior TIA = Unknown, then CVD = Unknown.
  - Else CVD = No.

## **2.4 Treatments (study treatment, rescue medication, concomitant therapies, compliance)**

### **2.4.1 Study treatment / compliance**

Study drug administration will be summarized for the Safety Population overall and by treatment group of the feeder studies. The summary will include

- The number and percentage of subjects dosed at each visit
- The number and percentage of subjects administered 0, 1, 2, ... doses, and total number of doses administered
- The number and percentage of injections at each injection site location (with total number of administered doses as the denominator for the percentage)
- The number and percentage of injections with each injection volume (with total number of administered doses as the denominator for the percentage)
- The number and percentage of subjects who missed 0, 1, 2, ... doses, and total number of missed doses. As per protocol, ORION-3 rollover subjects do not receive study medication on Day 1, thus ORION-3 rollover subjects who did not receive study medication on Day 1 do not count toward missed doses.

- The number and percentage of missed injections with each reason of not administering study drug (with total number of missed doses as the denominator for the percentage)

The duration of exposure (days) to inclisiran and the total subject-years of exposure in ORION-8 will be summarized for the Safety Population overall and by treatment group of the feeder studies.

The duration of exposure to inclisiran is defined as the number of days from Day 1 of ORION-8 to the earliest of the following:

- Last recorded contact/participation date of ORION-8
- Last study drug administration date in ORION-8 (if any) + 180 days

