4.4 Withdrawal Criteria

All subjects have the right to withdraw from the study at any point during treatment without prejudice. The investigator can discontinue any subject at any time if medically necessary. It will be documented whether or not each subject completed the clinical study. If study treatment or observations were discontinued, the reason will be recorded and the Sponsor should be notified promptly. The reasons that a subject may discontinue participation in a clinical study could be from one or more of the following:

- AE(s)
- Death
- Subject withdrew consent
- Physician decision
- Lost to follow-up
- Initiation of protocol-prohibited lipid-lowering therapy (eg, an approved PCSK9 inhibitor)

The applicable reason(s) above will be recorded in the eCRF and subjects should be encouraged to complete the EOS visit. All data collected up until the time of subject withdrawal is to be entered into the electronic case report form (eCRF). Any withdrawn subjects will not be replaced in this study. No further follow-up is allowed with the subject to collect additional information following discontinuation from the trial.

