4.4.1 Individual Subject Dosing Stopping Criteria

During the study subjects will have clinic visits at regular intervals. Dosing with inclisiran should be temporarily discontinued or stopped in subjects with:

1. Intolerable AEs, or if the investigator believes that continuing dosing will be detrimental to the subject's mental or physical health. This includes severe or serious reactions at the injection site and any anaphylactic type reactions.
2. Unexplained increases in transaminases (ALT or AST) or total bilirubin as follows:
 - a. ALT or AST >8xULN

- b. ALT or AST >5xULN for more than 2 weeks
- c. ALT or AST >3xULN and (total bilirubin >2xULN or INR >1.5)
- d. ALT or AST >3xULN with the appearance of fatigue, nausea, vomiting, right upper quadrant pain or tenderness, fever, rash, and/or eosinophilia (>5%)

The investigator should evaluate to see if other causes for the laboratory abnormalities are immediately apparent, such as obstructive gall bladder or bile duct disease, viral or alcoholic hepatitis, malignancy involving the liver, congestive hepatopathy, other hepatotoxins or heritable disorders.

- 3. Unexplained creatine kinase (CK) values >5 x ULN confirmed by repeat test when the CK elevation is associated with muscle pain, muscle tenderness and/or muscle weakness, or new onset renal dysfunction.

In the case that study medication is permanently discontinued the subject will be asked to return to complete an EOS visit, which should occur at least 90 days following the last dose of inclisiran.

All subjects should be followed until all clinically significant laboratory abnormalities return to normal or to the baseline state. Subjects discontinuing the trial due to withdrawal of consent or initiation of other PSCK9 lipid lowering therapies will not be followed up within the trial.

5 Treatment of Subjects

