5.4 Restrictions

Subjects will have to comply with the following restrictions during the study:

- Fasted for at least 8 hours for all visits for fasting lipids and glucose blood samples
- Blood donation will not be allowed at any time during the study
- Must refrain from unaccustomed strenuous physical exercise for 48 hours before the screening and any study visit until the follow-up has been completed

6 Schedule and sequence of procedures

The Schedule of Events/Assessments ([Table 6-1](#)) summarizes the study assessments by time point.

This study will be a long-term extension study for subjects considered “completers” of the Phase II lipid lowering MDCO-PCS-16-01 (ORION-3) or Phase III lipid lowering ORION feeder studies [MDCO-PCS-17-03 (ORION-9), MDCO-PCS-17-04 (ORION-10), or MDCO-PCS-17-08 (ORION-11)]. A “completer” of the previous study is defined as having received the final protocol dose of study drug and completing the final study visit/and being considered a successful completion during the EOS visit. The EOS visit in the previous feeder study will be Day 1 in

ORION-8 trial except for subjects enrolled in Sweden (Section 3.1 and Section 6.3). The expected duration of the subjects' involvement in the study will be a maximum of 3 years.

On Day 1 (EOS visit in the feeder study), subjects will receive blinded study medication except for subjects moving over from ORION-3. These subjects will receive the first study medication at day 90. Subjects who received placebo in the previous Phase III feeder study will receive blinded inclisiran and subjects who received inclisiran in the previous feeder study will receive blinded placebo at this visit, in order to maintain the blinding of the feeder study until database lock of those studies.

On Day 90, all subjects will receive inclisiran sodium 300 mg which is equivalent to 284 inclisiran. This is 180 days after the last injection in the previous feeder study for subjects that received inclisiran and will be the second dose of inclisiran for the subjects that received placebo in the feeder study.

The three study periods are:

- Study Entry (Day 1):
 - The EOS visit procedures from the previous ORION feeder study will be used as the Day 1 data for this study except for subjects enrolled in Sweden (Section 3.1 and Section 6.3). In addition, consent and eligibility assessment for this study will be completed.
- Treatment Phases:
 - Double Blind: Day 1 (blinded inclisiran or blinded placebo) to Day 90

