### 1.1 Study design

This study will be a long-term extension of the Phase II lipid lowering trial CKJX839A12201E1 (ORION-3; MDCO-PCS-16-01), which is the extension study of CKJX839A12201 (ORION-1; MDCO-PCS-15-01), and Phase III lipid-lowering studies CKJX839A12303 (ORION-9; MDCO-PCS-17-03), CKJX839A12304 (ORION-10; MDCO-PCS-17-04), and CKJX839A12305 (ORION-11; MDCO-PCS-17-08). This trial will be a global, multicenter study in approximately 300 centers. Up to 3300 subjects with atherosclerotic cardiovascular disease (ASCVD), ASCVD-risk equivalents (e.g., diabetes and familial hypercholesterolemia), or heterozygous familial hypercholesterolemia (HeFH) and elevated LDL-C despite treatment with LDL-C lowering therapies who are eligible and willing to participate may be enrolled. The objective of the study is to evaluate the efficacy, safety, and tolerability of long-term dosing of inclisiran. Informed consent will be obtained from subjects before the initiation of any study-specific procedures. The End of Study (EOS) visit in the previous feeder studies will be Day 1 in this extension trial except for subjects enrolled in Sweden. Sweden Specific Protocol Amendment 1 (to Global Amendment 1 version, dated 1 Nov 2018) was implemented to allow limited lab tests to be done on Day 1 and to collect any safety information during the gap between feeder's EOS and Day 1 of this study until ethics committee approval was granted in that country.

Subjects rolled over from the Phase III studies (ORION-9/10/11) will receive blinded inclisiran sodium 300 mg which is equivalent to 284 mg inclisiran, or blinded placebo on Day 1 in this trial. Subjects who received placebo in the previous Phase III feeder studies will receive blinded inclisiran and subjects who received inclisiran in the previous Phase III feeder studies will receive blinded placebo at this visit, in order to

- maintain the blinding of the feeder studies until database lock of those studies,
- maintain the semi-annual dosing schedule for subjects who received inclisiran in the previous Phase III feeder studies,

- administer the first two doses of inclisiran on the three-monthly initial dosing schedule for subjects who received placebo in the previous Phase III feeder studies.

All subjects will return at Day 90 for the next visit and will receive open label inclisiran sodium 300 mg.

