### 2.1.1 General definitions

#### Study drugs

The study drugs in this trial are the following:

- Investigational drug: Inclisiran will be administered as a single subcutaneous (SC) injection of 300 mg inclisiran sodium (equivalent to 284 mg inclisiran)/1.5 mL pre-filled syringe.
- Placebo: Placebo pre-filled syringes will contain saline solution and will be blinded and look identical to the inclisiran pre-filled syringes. Placebo will be administered as a 1.5 mL SC injection to match the dose of inclisiran.

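### The SAP lets a placebo injection extend exposure to inclisiran and sets no dose-based end for undosed ORION-3 rollovers; separately, its statement that no protocol analysis changed is wrong on at least four points

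*SAP*

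**What the plan says.** **Exposure.** SAP 2.4.1 defines the duration of exposure to inclisiran as the days from ORION-8 Day 1 to the earlier of the last recorded contact and "Last study drug administration date in ORION-8 (if any) + 180 days". SAP 2.1.1 introduces its list with "The study drugs in this trial are the following". The first entry is inclisiran and the second begins "Placebo: Placebo pre-filled syringes will contain saline solution". SAP 1.1 states that "subjects who received inclisiran in the previous Phase III feeder studies will receive blinded placebo at this visit", meaning Day 1.

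Protocol section 6 says of the Day 90 dose: "This is 180 days after the last injection in the previous feeder study for subjects that received inclisiran". ORION-3 rollovers get nothing on Day 1 and are first dosed at Day 90. Protocol 3.1 explains: "This is to maintain their 6 months dosing schedule on inclisiran treatment". SAP 2.2 nevertheless admits them to the Safety Population on consent alone.

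**Changes from the protocol.** SAP section 4 declares that there were none. The relevant protocol text is in 10.2.2 (safety population), 10.3.1 (baseline characteristics), 10.3.2 (medications) and 10.3.4.2 (laboratory tests).

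**The concern.** The quantity is labelled exposure to inclisiran, but its dose-based end is triggered by any study drug. For one group the first ORION-8 study drug is saline. If no inclisiran follows, the saline injection opens a 180-day window. The SAP's own 180-day convention, applied to the last real dose, would close earlier. For an ORION-3 rollover with no ORION-8 injection, the dose-based term drops out altogether.

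Long-term safety is one of the two primary objectives, and subject-years of exposure are the context in which the descriptive safety tables are read. The figure should mean what its label says.

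The section 4 statement matters for a different reason. A reader uses that section to learn where the analysis departs from the protocol, and here it points to nothing.

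**Working it through.** The documents give no exposure total to reproduce, so the check applies the rule to each type of subject.

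**Inputs**
- SAP end of exposure: the earlier of last contact C and last study drug + 180 days; C alone if no study drug was given (SAP 2.4.1).
- Last feeder inclisiran dose: 90 − 180 = about Day −90 (protocol section 6; protocol 3.1 implies the same for ORION-3).
- End of that dose's 180-day cover: about Day 90. If g days separate feeder EOS from ORION-8 Day 1, cover ends at about Day 90 − g. SAP 2.1.1 says that some Phase III rollovers have such a gap, and protocol 6.3 describes the Swedish case. The documents do not give g.

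Days are nominal; strict day counting moves results by about one day. The values of C and g are illustrations.

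**Inclisiran-Inclisiran, Day 1 placebo only**

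Excess = max(0, min(C, 180) − max(0, 90 − g)).

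With g = 0:
- C = 90: 0 days.
- C = 120: 120 − 90 = 30 days; 30/365.25 = 0.08 subject-years.
- C = 150: 150 − 90 = 60 days; 0.16 subject-years.
- C of 180 or more: 180 − 90 = 90 days; 0.25 subject-years.

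With C of 180 or more and a gap:
- g = 30: 180 − 60 = 120 days; 0.33 subject-years.
- g = 90 or more: 180 − 0 = 180 days; 0.49 subject-years.

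**ORION-3 rollover, no ORION-8 dose**

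Excess = max(0, C − 90), taking the last ORION-3 dose at about Day −90.
- C = 90: 0 days.
- C = 120: 30 days; 0.08 subject-years.
- C = 180: 90 days; 0.25 subject-years.
- Beyond that it grows with C; last contact is the only limit.

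**Everyone else**
- Placebo-Inclisiran subjects receive inclisiran on Day 1, so every study drug they get in ORION-8 is inclisiran: excess 0.
- Any subject given open-label inclisiran has inclisiran as the last study drug: excess 0.
- For a completer last dosed at Day 990, 990 + 180 = Day 1170, later than Day 1080. Last contact decides: excess 0.

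**Order of magnitude, on assumptions only.** Take the 2991 subjects enrolled by February 2020 (protocol, Amendment 2 rationale). Assume that all are followed to Day 1080, that half are Inclisiran-Inclisiran, and that 0.5% to 5% of that half received only placebo, each with the full 90-day excess and no gap.
- Total: 2991 × 1079/365.25 = about 8836 subject-years.
- At 0.5%: 7.48 subjects × 0.246 = 1.8 subject-years, or 0.02%.
- At 5%: 74.8 × 0.246 = 18.4 subject-years, or 0.21%.

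The group split and the placebo-only share are not in the documents. Full follow-up overstates the total, so the percentages would be somewhat higher with drop-out.

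**Section 4, side by side**
1. *Safety Population.* Protocol 10.2.2 requires at least one dose of study drug. SAP 2.2 takes ORION-3 rollovers on consent.
2. *ORION-3 rollovers' baseline characteristics.* Protocol 10.3.1 names the ORION-3 study baseline. SAP 2.3.2 takes weight and BMI from the last ORION-3 weight, eGFR from the ORION-8 baseline, and height and race from ORION-1 screening.
3. *PCS laboratory values.* Protocol 10.3.4.2 conditions on the feeder baseline as well as on Day 1. SAP Appendix 5.3 uses the ORION-8 baseline only. Whether the protocol means two analyses or one joint condition, the SAP differs.
4. *Prior medication.* Protocol 10.3.2 promises a summary of medication taken before the feeder baseline. SAP 2.4.2 keeps the word in its title but specifies only new or changed medications and baseline lipid-modifying therapy.

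**The case against.** **The effect is almost nil, and the rule is only a convention.** The rule also runs through missed doses, and the words (if any) show that undosed subjects were foreseen. The size argument stands: this is a labelling and derivation error with little numerical weight. It does not rescue the definition, because a convention for exposure to inclisiran should not be started by saline.

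**Early stoppers leave before any excess can build up.** Protocol 4.4 says: "No further follow-up is allowed with the subject to collect additional information following discontinuation from the trial". This limits how many subjects are affected, but it does not show that the excess is near zero for most of them. Protocol 4.4.1 places the EOS visit by a minimum, "which should occur at least 90 days following the last dose of inclisiran", with no maximum. It also follows clinically significant laboratory abnormalities to resolution, and protocol 5.3.1 does so for adverse events. SAP 2.1.1 takes last contact from all collected data. Nothing in the documents gives the distribution of last contact.

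**Inflated safety rates.** A reader might infer these because exposure-adjusted incidence rate is in the SAP's abbreviation list. The SAP text specifies no such rate; its adverse event tables use numbers and percentages of subjects.

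**Changed treatment classification.** A reader might add to the section 4 list that the protocol classifies by actual treatment received and the SAP by feeder group. The documents do not establish a change. Protocol 10.2.2 does not say in which study the treatment was received, the SAP's Phase III groups use actual feeder treatment, and that treatment determines the planned Day 1 injection. This is a plausible specification of the protocol.

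**Concealment.** This is not supported either. SAP 2.2, 2.3.2 and Appendix 5.3 state the first three differences openly; only the prior-medication omission is silent. Some choices may well be sensible, and ORION-1 as the source for race is unlikely to alter any result. The fault is the declaration in section 4.

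**Conclusion.** Both parts hold, at the level of something to consider.

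The exposure rule as written can credit time after a placebo injection that the SAP's own 180-day convention does not cover, and it leaves undosed ORION-3 rollovers limited only by last contact. For a placebo-only Inclisiran-Inclisiran subject the excess is at most about 90 days, plus the length of any gap up to 90 days. This rests on nominal visit timing and on the 180-day convention being applied to the last feeder dose. The number of subjects affected is not in the documents, so no trial-level total is claimed. The effect is likely very small and is confined to the exposure summary.

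Section 4 is incorrect on at least four points where the protocol and SAP can be compared directly. Four is a minimum, not a complete count.

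**What to change.** **Exposure.** In SAP 2.4.1, define duration as max(0, min(last contact, last inclisiran dose + 180 days) − ORION-8 Day 1). The last inclisiran dose is the last ORION-8 inclisiran injection. If there was none, use the actual date of the last feeder inclisiran injection. Placebo does not count. The floor of zero is needed because a gap of more than about 90 days would put the end of cover before Day 1. The change is one derivation. Protocol section 9 allows certain feeder data to be imported, and SAP 2.1.1 already relies on feeder dosing dates for the feeder baseline.

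**Section 4.** Replace the statement with a list of the four differences and a reason for each, after a line-by-line comparison with protocol sections 10.2 and 10.3. Items to examine, not counted here:
- hsCRP among the efficacy parameters (SAP 2.6.1 against protocol 7.2);
- no urinalysis summary in SAP 2.7.3;
- no stated end to the treatment-emergent period in SAP 2.7.1 (against protocol 10.2.3).

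If the database is already locked, the list can go in the study report.

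No new table is needed and no event leaves the safety tables. The count of ORION-3 rollovers with no ORION-8 dose needs no footnote, because SAP 2.4.1 already tabulates subjects by number of doses, starting at 0, within each feeder group.
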